Appendix E International Prognostic Scoring System for MDS

Variable					
Score	0	0.5	1.0	1.5	2.0
BM Blasts	<5	5-10		11-20	31-30
Karyotype	Good	Intermediate	Poor		
Cytopenias	0/1	2/3			

Risk Group	Score	Med Survival (y)	25% AML progression (y)
Low	0	5.7	9.4
Int-1	0.5-1.0	3.5	3.3
Int-2	1.5-2.0	1.1	1.1
High	>2.5	0.4	0.2

- Cytopenias are designated by the following: ANC<1800, platelets< 100K, Hg<10g
- Karyotype risk groups:
 - Good: Normal (46 XX or 46 XY), isolated -Y, isolated del(5q), or isolated del(20q)
 - Intermediate: All karyotypes not otherwise designated good or poor
 - Poor: complex karyotype (≥3 abnormalities) or any chromosome 7 abnormalities

PROTOCOL TITLE: I 49217 - Phase 1 CDX-1401/ Poly-ICLC +Decitabine +Nivolumab in Patients with MDS or Low Blast Count AML

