3 INCLUSION AND EXCLUSION CRITERIA

3.1 Inclusion Criteria

Subjects who present with a suspected or confirmed diagnosis of MDS/AML, and who are interested in potential participation on a clinical trial, will be screened for enrollment. Only patients who are willing to sign a written informed consent form will be screened. Patients must undergo bone marrow aspirate and biopsy with sample acquisition for protocol screening.

To be included in this study, participants must meet the following criteria:

1. Have a confirmed diagnosis of:

PROTOCOL TITLE: I 49217 - Phase 1 CDX-1401/ Poly-ICLC +Decitabine +Nivolumab in
Patients with MDS or Low Blast Count AML

- a. IPSS intermediate-1, intermediate-2 or high-risk MDS including Chronic Myelomonocytic Leukemia (CMML) **OR**
 - b. Low blast count AML with $\leq 30\%$ blasts previously classified as Refractory Anemia with excess blasts in transformation.
2. Age ≥ 18 years of age.
 3. Have an ECOG Performance Status of ≤ 2 . Refer to **Appendix C**.
 4. Have adequate organ function defined by the following laboratory values:
 - Hepatic:
 - Total bilirubin ≤ 3 X upper limit of normal (ULN) (except subjects with Gilbert Syndrome, who can have total bilirubin up to 3.5 X ULN)
 - Aspartate Transaminase (AST/SGOT) and Alanine Transaminase (ALT/SGPD) ≤ 3 X ULN
 - Renal:
 - Serum creatinine ≤ 2.5 X ULN
 - Cardiac:
 - Troponin-I, CK-MB \leq ULN
 - LVEF \geq LLN (institutional limit)
 5. Participants of child-bearing potential must agree to use adequate contraceptive methods (e.g., hormonal or barrier method of birth control; abstinence) prior to study entry. Should a woman become pregnant or suspect she is pregnant while she or her partner is participating in this study, she should inform her treating physician immediately.
 6. Participant or legal representative must understand the investigational nature of this study and sign an Independent Ethics Committee/Institutional Review Board approved written informed consent form prior to receiving any study related procedure.
 7. No prior exposure to nivolumab.
 8. No prior investigational therapy within 2 weeks prior to study enrollment.

Refer to **Appendix A** for the **ELIGIBILITY VERIFICATION FORM: INCLUSION CRITERIA** checklist.

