Appendix F Revised International Prognostic Scoring System

[figure not shown]
Prognostic Group	Cytogenetic Abnormality
Very Good	-Y, del(11q)
Good	NL, del(5q), del(20q), ≤2 w/del (5q)
Int	del(7q), +8, +19, i(17q), any other ≤2 clones
Poor	-7, inv(3)/t(3q)/del(3q), ≥2 w/ -7/del(7q), complex ≤3
Very Poor	Complex (> 3 abnormalities)

Variable	0	0.5	1	1.5	2	3	4
cytogenetics	VG		G		I	P	VP
BM blasts%	≤2		>2-<5		5-10	>10	
Hg (g)	≥10		8-10	<8			
Platelets(/uL)	≥100K	50-100K	<50				
ANC (/uL)	≥0.8	<0.8					

Risk Group	Score	Survival (y)	25% AML Tx (y)
V. Low	≤1.5	8.8	NR
Low	>1.5-3	5.3	10.8
Int	>3-4.5	3.0	3.2
High	>4.5-6	1.6	1.4
V. High	>6	0.8	0.73

PROTOCOL TITLE: I 49217 - Phase 1 CDX-1401/ Poly-ICLC +Decitabine +Nivolumab in Patients with MDS or Low Blast Count AML

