- 18 At the end of cycle 1 a Bone Marrow aspirate is to be done purely for collection of correlative specimens (see Section 11.9.2) unless the patient has demonstrated sufficient clinical response to warrant disease assessment at the discretion of the treating physician. **Note:** At the end of Cycle 1, if a bone marrow aspirate is not able to be done, a bone marrow biopsy may be performed instead. Thereafter, a complete bone marrow assessment to be done every 4th cycle (per standard of care) for response assessment.
- 19 Testing for HIV I/II Ab, HBsAg, HCV Ab+/- PCR should be done only in patients for whom there is a concern for prior infection with one of these viral pathogens. Testing is NOT required if there is no history of infection.
- 20 Refer to Appendix E and Appendix F for calculation instructions.
- 21 Bone marrow biopsy per institutional guidelines for patients on study < 2 years. Bone marrow biopsy every 6 months (\pm 2 months) for patients on study for \geq 2 years with correlative samples. Correlative samples to be collected at any time point when patient has a bone marrow biopsy for standard of care.

PROTOCOL TITLE: I 49217 - Phase 1 CDX-1401/ Poly-ICLC +Decitabine +Nivolumab in
Patients with MDS or Low Blast Count AML

PROTOCOL TITLE: I 49217 - Phase 1 CDX-1401/ Poly-ICLC +Decitabine +Nivolumab in
Patients with MDS or Low Blast Count AML

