3. PARTICIPANT REGISTRATION

The participant completes the Gender, Race, and Ethnicity Form and this is placed in the study binder.

RPCI does not grant exceptions to eligibility criteria.

Phase 1 Protocol Registration Instructions

Contact the RPCI Network Monitor to verify that a slot is available in the open cohort when a participant has been identified. **Do not have the participant sign consent prior to verifying an open slot.**

- After the participant signs consent, the Subject Screening and Enrollment Log must be faxed or emailed to the RPCI Network Monitor within 1 business day. The RPCI Network

PROTOCOL TITLE: I 49217 - Phase 1 CDX-1401/ Poly-ICLC +Decitabine +Nivolumab in
Patients with MDS or Low Blast Count AML

Monitor will confirm receipt of the Subject Screening and Enrollment Log and email the participant ID number.

- When the participant has met eligibility, a signed eligibility checklist and other requested documentation will be faxed or emailed to the RPCI Network Monitor.
- Within 1 business day of receipt of the eligibility check list, the RPCI Network Monitor will fax or email the cohort assignment and dose level.
- An email must be sent by the site to confirm receipt of the cohort assignment and to provide the planned treatment start date.

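### As printed, the Appendix E IPSS table gives no risk group to a total of exactly 2.5 and no score to 21-30% blasts, leaving a literal eligibility gap and missing risk labels

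*Combined protocol and SAP*

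**What the plan says.** Inclusion criterion 1a in Section 3.1 admits "IPSS intermediate-1, intermediate-2 or high-risk MDS including Chronic Myelomonocytic Leukemia (CMML"), so of the four IPSS groups only Low is left out. Criterion 1b, joined to it by OR, admits low blast count AML with up to 30% blasts and asks for no IPSS score.

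Section 11.2 lists the IPSS/IPSS-R among the items for confirming eligibility and sends the calculation to Appendices E and F. Appendix J, note 20, repeats this: "Refer to Appendix E and Appendix F for calculation instructions". Sections 11.7 and 11.8 require the score again at Cycle 5 Day 1, every fourth cycle thereafter and end of treatment.

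Appendix E sets Low at 0 and continues "Int-1 0.5-1.0 3.5 3.3", "Int-2 1.5-2.0 1.1 1.1" and "High >2.5 0.4 0.2"; in each row the score comes first. Its blast row reads "BM Blasts <5 5-10 11-20 31-30", where the last band is the 2.0-point column.

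The participant registration section of the network-site instructions (Appendix K) states that "RPCI does not grant exceptions to eligibility criteria". In Appendix F the neutrophil row reads "ANC (/uL) ≥0.8 <0.8".

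**The concern.** A table used to confirm eligibility should give every attainable score a group and every admissible blast percentage a score. This one does neither.

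A patient at 2.5 lies above intermediate-2 and below the printed High threshold. Criterion 1a requires a named group, and the Appendix A checklist needs Yes or N/A on every line. Taken at its word, the table turns this patient away while admitting one who scores lower (2.0) and one who scores higher (3.0). A patient with 21-30% blasts cannot be scored at all.

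Two things are at stake: a clean eligibility record for the 2.5 patients, and consistent baseline and follow-up risk labels in a study of at most 18 evaluable participants.

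**Working it through.** **Inputs (Appendix E).**
- Blasts: below 5% = 0; 5-10% = 0.5; 11-20% = 1.5; the 2.0-point band is printed 31-30.
- Karyotype: good = 0; intermediate = 0.5; poor = 1.0.
- Cytopenias: 0/1 = 0; 2/3 = 0.5.
- Groups: Low 0; Int-1 0.5-1.0; Int-2 1.5-2.0; High above 2.5.

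**Method.** Total = blasts + karyotype + cytopenias. There are 4 × 3 × 2 = 24 combinations. The plan gives no figure of its own to reproduce here. For the enumeration the broken band is read as 21-30%.

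Karyotype plus cytopenias gives six sums: 0, 0.5, 0.5, 1.0, 1.0 and 1.5. Adding each blast score:

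| Blasts | Six totals | Groups as printed |
|---|---|---|
| below 5% | 0, 0.5, 0.5, 1.0, 1.0, 1.5 | 1 Low, 4 Int-1, 1 Int-2 |
| 5-10% | 0.5, 1.0, 1.0, 1.5, 1.5, 2.0 | 3 Int-1, 3 Int-2 |
| 11-20% | 1.5, 2.0, 2.0, 2.5, 2.5, 3.0 | 3 Int-2, **2 none**, 1 High |
| 21-30% | 2.0, 2.5, 2.5, 3.0, 3.0, 3.5 | 1 Int-2, **2 none**, 3 High |

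**Result, all 24 combinations.** 1 Low, 7 Int-1, 8 Int-2, 4 High and 4 with no group. Every total is a multiple of 0.5, so 2.5 is the only attainable value that falls between groups.

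**Result, blasts at or below 20% (18 combinations).** 1 Low, 7 Int-1, 7 Int-2, 1 High and 2 with no group. Three combinations reach 2.5 or more, and two of the three have no group:
- 11-20% blasts, intermediate karyotype, 2/3 cytopenias: 1.5 + 0.5 + 0.5 = 2.5.
- 11-20% blasts, poor karyotype, 0/1 cytopenias: 1.5 + 1.0 + 0 = 2.5.

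**Blast band read literally.** No percentage lies in 31-30, so all 6 combinations with 21-30% blasts have no score.

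**After repair.** With 2.5 placed in High and the band set to 21-30, the counts are 1 Low, 7 Int-1, 8 Int-2 and 8 High. All 24 are classified, and the 23 above Low are in groups that criterion 1a admits. Placing 2.5 in Int-2 instead would leave eligibility unchanged.

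**Appendix F neutrophils.** The header unit is per microlitre and the cut is 0.8. Taken literally, a count of 500/uL is at least 0.8 and scores 0. If the cut is in thousands (0.8 × 1,000 = 800/uL), the same patient scores 0.5. Appendix E puts its own neutrophil cut at 1800, which supports the second reading.

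**The case against.** A reader might infer that higher-risk MDS patients are ineligible under this plan, or that the enrolled population will depend on who did the scoring. The documents do not support either.

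- **Eligibility at 2.5.** The score lies between two admitted groups. Either way of closing the gap makes the patient eligible, and only a strictly literal reading excludes. Criterion 1a names the IPSS without citing Appendix E; the link runs through Section 11.2 and note 20.
- **Eligibility at 21-30% blasts.** Criterion 1b is a separate route that needs no score, and Section 2.1 counts low blast count AML within the intermediate-2/high designation for this study. The broken band costs those patients a score, not entry.
- **Analysis.** Nothing in Section 19 uses the risk group, and Section 19.5 does not name the IPSS. Counts of score combinations are not patient frequencies, so they do not show how many participants are affected.
- **Text extraction.** The High threshold may be a greater-or-equal sign lost when the PDF was read.

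The first three stand and set the severity. The fourth stands as a caution. A greater-or-equal sign survives in the same appendix, in the definition of a complex karyotype, and a lost sign would not explain 31-30, but a misread digit cannot be excluded from the text alone.

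On Appendix F, the table uses shorthand elsewhere (a platelet cell reads below 50 beside 50-100K), and the IPSS-R is not an entry criterion. That item is therefore minor.

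**Conclusion.** The point holds in a limited form. As printed, Appendix E assigns no group to a total of 2.5 and no score to 21-30% blasts. Two of the three combinations at or above 2.5 with blasts at or below 20% are unclassifiable and, read literally, fail criterion 1a. Patients with 21-30% blasts who meet criterion 1b can enter, but the required baseline and follow-up IPSS cannot be calculated for them.

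The consequence is a literal eligibility gap plus missing or inconsistent descriptive labels. The DLT rule, sample size and primary analysis are unaffected. Severity is minor. The conclusion assumes that the extracted text matches the original PDF in the two cells concerned.

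**What to change.** Check the two Appendix E cells against the source PDF. If they stand as extracted:

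- Make the risk groups continuous. The table's own half-point steps imply that High starts at 2.5, that is, ≥2.5.
- Correct the 2.0-point blast band. The preceding band (11-20) and the 30% cap in criterion 1b imply 21-30.
- As a minor item, state the Appendix F neutrophil cut-off in the units of its header (0.8 read in thousands is 800/uL).

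The cost is two table cells and one unit in the next amendment, with no new data or patients. Any IPSS label already recorded for a total of 2.5 or for 21-30% blasts can be checked at the same time.

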Appendix F Revised International Prognostic Scoring System

[figure not shown]
Prognostic Group	Cytogenetic Abnormality
Very Good	-Y, del(11q)
Good	NL, del(5q), del(20q), ≤2 w/del (5q)
Int	del(7q), +8, +19, i(17q), any other ≤2 clones
Poor	-7, inv(3)/t(3q)/del(3q), ≥2 w/ -7/del(7q), complex ≤3
Very Poor	Complex (> 3 abnormalities)

Variable	0	0.5	1	1.5	2	3	4
cytogenetics	VG		G		I	P	VP
BM blasts%	≤2		>2-<5		5-10	>10	
Hg (g)	≥10		8-10	<8			
Platelets(/uL)	≥100K	50-100K	<50				
ANC (/uL)	≥0.8	<0.8					

Risk Group	Score	Survival (y)	25% AML Tx (y)
V. Low	≤1.5	8.8	NR
Low	>1.5-3	5.3	10.8
Int	>3-4.5	3.0	3.2
High	>4.5-6	1.6	1.4
V. High	>6	0.8	0.73

PROTOCOL TITLE: I 49217 - Phase 1 CDX-1401/ Poly-ICLC +Decitabine +Nivolumab in Patients with MDS or Low Blast Count AML

Rule out non-inflammatory causes. If non-inflammatory cause, treat accordingly and continue I-O therapy

Patients on IV steroids may be switched to an equivalent dose of oral corticosteroids (e.g. prednisone) at start of tapering or earlier, once sustained clinical improvement is observed. Lower bioavailability of oral corticosteroids should be taken into account when switching to the equivalent dose of oral corticosteroids.

Pulmonary Adverse Event Management Algorithm

[figure not shown]
Rule out non-inflammatory causes. If non-inflammatory cause, treat accordingly and continue I-O therapy. Evaluate with imaging and pulmonary consultation.

Patients on IV steroids may be switched to an equivalent dose of oral corticosteroids (e.g. prednisone) at start of tapering or earlier, once sustained clinical improvement is observed. Lower bioavailability of oral corticosteroids should be taken into account when switching to the equivalent dose of oral corticosteroids.

Hepatic Adverse Event Management Algorithm

Rule out non-inflammatory causes. If non-inflammatory cause, treat accordingly and continue I-O therapy. Consider imaging for obstruction.

[figure not shown]
Patients on IV steroids may be switched to an equivalent dose of oral corticosteroids (e.g. prednisone) at start of tapering or earlier, once sustained clinical improvement is observed. Lower bioavailability of oral corticosteroids should be taken into account when switching to the equivalent dose of oral corticosteroids.

*I-O therapy may be delayed rather than discontinued if AST/ALT ≤ 8 x ULN or T.bili ≤ 5 x ULN.

**The recommended starting dose for grade 4 hepatitis is 2 mg/kg/day methylprednisolone IV.

Endocrinopathy Management Algorithm

[figure not shown]
Rule out non-inflammatory causes. If non-inflammatory cause, treat accordingly and continue I-O therapy. Consider visual field testing, endocrinology consultation, and imaging.

Patients on IV steroids may be switched to an equivalent dose of oral corticosteroids (e.g. prednisone) at start of tapering or earlier, once sustained clinical improvement is observed. Lower bioavailability of oral corticosteroids should be taken into account when switching to the equivalent dose of oral corticosteroids.

Skin Adverse Event Management Algorithm

Rule out non-inflammatory causes. If non-inflammatory cause, treat accordingly and continue I-O therapy.

[figure not shown]
Patients on IV steroids may be switched to an equivalent dose of oral corticosteroids (e.g. prednisone) at start of tapering or earlier, once sustained clinical improvement is observed. Lower bioavailability of oral corticosteroids should be taken into account when switching to the equivalent dose of oral corticosteroids.

*Refer to NCI CTCAE v4 for term-specific grading criteria.

^If SJS/TEN is suspected, withhold I-O therapy and refer patient for specialized care for assessment and treatment. If SJS or TEN is diagnosed, permanently discontinue I-O therapy.

Neurological Adverse Event Management Algorithm

Rule out non-inflammatory causes. If non-inflammatory cause, treat accordingly and continue I-O therapy.

Patients on IV steroids may be switched to an equivalent dose of oral corticosteroids (e.g. prednisone) at start of tapering or earlier, once sustained clinical improvement is observed. Lower bioavailability of oral corticosteroids should be taken into account when switching to the equivalent dose of oral corticosteroids.

PROTOCOL TITLE: I 49217 - Phase 1 CDX-1401/ Poly-ICLC +Decitabine +Nivolumab in Patients with MDS or Low Blast Count AML

Appendix I Nivolumab Monotherapy Adverse Drug Reactions

Adverse drug reactions in patients treated with nivolumab monotherapy in clinical studies (N= 9, 212), Investigator Brochure, v16, Table 5.6.1-1.

System Organ Class	Preferred Term	Overall Frequency N (%)	Serious ADRs N (%)	Life Threatening ADRs N (%)	Fatal ADRs N (%)
Cardiac Disorder	Tachycardia	Uncommon n 17 (0.18)	n	n	n
	Arrhythmia (including Ventricular arrhythmia, atrial fibrillation ^a)	Uncommon n 9 (0.10)	Y 3 (0.03)	n	n
Ear and Labyrinth Disorders	Vertigo	Uncommon n 22 (0.24)	n	n	n
Endocrine Disorders	Hypothyroidism (including Autoimmune hypothyroidism)	Common 443 (4.81)	Y 14 (0.14)	n	n
	Hyperthyroidism	Common 141 (1.53)	Y 5 (0.05)	n	n
	Hyperglycemia	Uncommon n 72 (0.78)	Y 16 (0.17)	Y^b 1 (0.01)	n
	Adrenal Insufficiency	Uncommon n 52 (0.56)	Y 28 (0.31)	Y^b 1 (0.01)	n
	Thyroiditis (including Autoimmune thyroiditis)	Uncommon n 36 (0.39)	Y^b 1 (0.01)	n	n
	Hypophysitis	Uncommon n 32 (0.35)	Y 16 (0.17)	n	n
	Diabetes mellitus	Uncommon n 19 (0.21)	Y 4 (0.04)	n	n
	Hypopituitarism	Uncommon n 16 (0.17)	Y 5 (0.05)	n	n
	Diabetic ketoacidosis	Rare 3 (0.03)	Y 3 (0.03)	Y^b 1 (0.01)	n
	Eye Disorders	Dry eye ^a	Uncommon n 42 (0.46)	n	n
Vision blurred ^a		Uncommon n 32 (0.35)	n	n	n
Uveitis (including iridocyclitis)		Uncommon n 15 (0.16)	Y 3 (0.03)	n	n
Gastrointestinal	Diarrhea	Common	Y	n	n

PROTOCOL TITLE: I 49217 - Phase 1 CDX-1401/ Poly-ICLC +Decitabine +Nivolumab in Patients with MDS or Low Blast Count AML

System Organ Class	Preferred Term	Overall Frequency N (%)	Serious ADRs N (%)	Life Threatening ADRs N (%)	Fatal ADRs N (%)
Disorders		783 (8.50)	68 (0.74)		
	Nausea	Common 783 (8.50)	Y 23 (0.25)	n	n
	Vomiting	Common 700 (7.60)	Y 26 (0.28)	n	n
	Constipation	Common 223 (2.42)	n	n	n
	Abdominal Pain	Common 222 (2.41)	Y 13 (0.14)	n	n
	Stomatitis (including Mucosal inflammation, Mucosal ulceration, Mouth ulceration)	Common 159 (1.73)	Y 9 (0.10)	n	n
	Dry mouth	Common 157 (1.70)	n	n	n
	Colitis (including Autoimmune colitis)	Common 103 (1.12)	Y 72 (0.78)	n	Y 2 (0.02)
	Pancreatitis(including Autoimmune pancreatitis, Pancreatitis acute)	Uncommo n 19 (0.21)	Y 10 (0.11)	n	n
	Gastritis (including Gastritis erosive)	Uncommo n 16 (0.17)	Y 4 (0.04)	n	n
General disorders and administration site conditions					
	Fatigue (including Asthenia)	Very Common 1701 (18.47)	Y 30 (0.33)	n	n
	Pyrexia	Common 326 (3.54)	Y 41 (0.45)	n	n
	Edema (including Edema peripheral, Generalized edema, Peripheral swelling, Localized edema, Periorbital edema, Face edema, Swelling face)	Common 182 (1.98)	Y 5 (0.05)	n	n
	Chills ^a	Common 146 (1.58)	Y 4 (0.04)	n	n
Hepatobiliary Disorders	Hepatitis (including Autoimmune hepatitis, Hepatitis acute)	Uncommo n 32 (0.35)	Y 25 (0.27)	Y ^b 1 (0.01)	n
Immune System Disorders	Infusion related reaction	Common 152 (1.65)	Y 21 (0.23)	Y ^b 1 (0.01)	n
	Hypersensitivity	Uncommo n 70 (0.76)	Y 9 (0.10)	Y ^b 1 (0.01)	n
	Anaphylactic reaction	Rare 4 (0.04)	Y 3 (0.03)	Y ^b 2 (0.02)	n
Infections and Infestations	Upper respiratory tract infection	Uncommo n 31 (0.34)n	n	n	n
	Bronchitis	Common	n	n	n

PROTOCOL TITLE: I 49217 - Phase 1 CDX-1401/ Poly-ICLC +Decitabine +Nivolumab in Patients with MDS or Low Blast Count AML

System Organ Class	Preferred Term	Overall Frequency N (%)	Serious ADRs N (%)	Life Threatening ADRs N (%)	Fatal ADRs N (%)
		10 (0.11)			
Investigations	Aspartate aminotransferase increased	Common 257 (2.79)	Y 23 (0.25)	n	n
	Alanine aminotransferase increased	Common 239 (2.59)	Y 27 (0.29)	n	n
	Lipase increased	Common 163 (1.77)	Y 13 (0.14)	n	n
	Blood alkaline phosphatase increased ^a	Common 127 (1.38)	Y 6 (0.07)	n	n
	Amylase increased	Common 102 (1.11)	Y 4 (0.04)	n	n
	Blood creatinine increased ^a	Common 100 (1.09)	Y 3 (0.03)	n	n
	Blood thyroid stimulating hormone increased ^a	Common 92 (1.00)	n	n	n
	Blood bilirubin increased	Uncommon 49 (0.53)	Y 4 (0.04)	n	n
Metabolism and Nutrition Disorders	Decreased appetite	Common 536 (5.82)	Y 5 (0.05)	n	n
	Hyponatremia	Uncommon 87 (0.94)	Y 17 (0.18)	n	n
Musculoskeletal and Connective Tissue Disorders	Musculoskeletal pain (including Back pain, Bone pain, Musculoskeletal chest pain, Musculoskeletal discomfort, Myalgia, Neck pain, Pain in extremity, Pain in jaw)	Common 427 (4.64)	Y 4 (0.04)		
	Arthralgia (including Arthritis, Polyarthritis, and Osteoarthritis)	Common 400 (4.34)	Y 10 (0.11)		
	Myositis (including Polymyositis) ^a	Rare 6 (0.07)	Y 4 (0.04)		
	Polymyalgia rheumatica	Rare 6 (0.07)	Y ^b 1 (0.01)		
	Rhabdomyolysis ^{a, b}	Rare 1 (0.01)	Y 1 (0.01)		Y 1 (0.01)
Nervous System Disorders	Headache	Common 215 (2.33)	Y 4 (0.04)	n	n
	Neuropathy peripheral (including Burning sensation, Peripheral motor neuropathy, Polyneuropathy, Peripheral sensory neuropathy)	Common 102 (1.11)	Y 9 (0.10)	n	n
	Dizziness	Uncommon 83 (0.90)	Y 3 (0.03)	n	n
	Cranial nerve disorder ^a	Uncommon	Y	n	n

PROTOCOL TITLE: I 49217 - Phase 1 CDX-1401/ Poly-ICLC +Decitabine +Nivolumab in Patients with MDS or Low Blast Count AML

System Organ Class	Preferred Term	Overall Frequency N (%)	Serious ADRs N (%)	Life Threatening ADRs N (%)	Fatal ADRs N (%)
		n 12 (0.13)	6 (0.07)		
	Myasthenic syndrome (including Myasthenia gravis)	Rare 3 (0.03)	Y 3 (0.03)	n	n
	Guillain-Barre syndrome	Rare 2 (0.02)	Y 2 (0.02)	n	n
	Demyelination (including Demyelinating polyneuropathy)	Rare 2 (0.02)	Y 2 (0.02)	n	n
	Encephalitis including Autoimmune encephalitis)	Rare 2 (0.02)	Y 2 (0.02)	n	Y ^b 1 (0.01)
Renal and Urinary Disorders	Renal failure (including Acute kidney injury)	Uncommon n 41 (0.45)	Y 24 (0.26)	Y 2 (0.02)	n
	Nephritis (including Autoimmune nephritis, Tubulointerstitial nephritis)	Uncommon n 14 (0.15)	Y 11 (0.12)	n	n
Respiratory, Thoracic, and Mediastinal Disorders	Pneumonitis (including Interstitial lung disease, Organizing pneumonia)	Common 276 (3.00)	Y 152 (1.65)	Y 7 (0.08)	Y 9 (0.10)
	Dyspnea	Common 231 (2.51)	Y 35 (0.38)	Y 1 (0.01)	Y 3 (0.03)
	Cough	Common 222 (2.41)			
	Respiratory failure (including Respiratory distress) ^a	Uncommon n 18 (0.20)	Y 16 (0.17)	Y 2 (0.02)	Y 7 (0.08)
	Lung infiltration	Rare 7 (0.08)	Y 2 (0.02)	n	n
Skin and Subcutaneous Tissue Disorders	Rash (including Rash maculopapular, Rash generalized, Rash erythematous, Rash pruritic, Rash follicular, Rash macular, Rash papular, Rash pustular, Rash vesicular, Dermatitis, Dermatitis acneiform, Dermatitis allergic, Dermatitis exfoliative, and Drug eruption)	Very Common 1010 (10.96)	Y 20 (0.22)	n	n
	Pruritus (including Pruritus generalized)	Common 722 (7.84)	Y 2 (0.02)	n	n
	Dry skin	Common 182 (1.98)	n	n	n
	Vitiligo	Common 99 (1.07)	n		
	Erythema	Uncommon n 75 (0.81)	n		
	Alopecia	Uncommon n 60 (0.65)	n		

PROTOCOL TITLE: I 49217 - Phase 1 CDX-1401/ Poly-ICLC +Decitabine +Nivolumab in Patients with MDS or Low Blast Count AML

System Organ Class	Preferred Term	Overall Frequency N (%)	Serious ADRs N (%)	Life Threatening ADRs N (%)	Fatal ADRs N (%)
	Urticaria	Uncommon 40 (0.43)	n		
	Psoriasis	Uncommon 18 (0.20)	Y 3 (0.03)		
	Erythema multiforme	Rare 7 (0.08)	Y 3 (0.03)		
	Rosacea	Rare 2 (0.02)	n		
	Toxic epidermal necrolysis	Rare 1 (0.01)	Y 1 (0.01)		Y 1 (0.01)
Vascular Disorders	Hypotension ^a	Uncommon 43 (0.47)	Y 5 (0.05)	n	n
	Hypertension	Uncommon 42 (0.46)	n	n	n
	Vasculitis	Rare 2 (0.02)	n	n	n

^a ADR not included in previous IB version 14.

^b Despite single reported occurrence, this event is considered to be ADR based on observed nivolumab safety profile across treatment groups.

